9.5 Study Size

In phase III studies investigating the interferon-free ABBVIE REGIMEN \pm RBV, SVR12 rates of at least 90% were observed, even in difficult-to-treat CHC patients (e.g. cirrhotic G1a treatment experienced patients). To describe in routine clinical practice the effectiveness of the ABBVIE REGIMEN \pm RBV in patients with CHC, a precise estimate of the SVR12 rates in the core population of this study should be achieved (see Section **Error! Reference source not found.** for the definition of the core population).

As obvious from Table 3, if the SVR12 rate is at least 90%, then with 158 evaluable patients the width of the 95% confidence interval (CI) will not be wider than 10%. If the SVR12 rate is at least 95%, then 94 patients are sufficient for a width of 10%. Therefore, 158 patients should be enrolled during the inclusion period of 8 months.

Table 3 Width of 95% Confidence Interval for SVR12

Number of patients	SVR12 rates	95% Confidence Interval*			Width
		Lower Limit	Upper Limit		
158	90%	84.2	94.2		10.0%
94	95%	88.4	98.4		10.0%

* exact two-sided 95% confidence interval according Clopper-Pearson

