9.7.3.3 Statistical Methods for Analysis of Effectiveness Variables

The simple percentage of patients achieving SVR12 will be calculated and an exact two-sided 95% confidence interval (CI) of the percentage will be computed based on the Clopper-Pearson method.

Corresponding methods will be used for other response rates (EoT response rate, relapse rate, viral breakthrough). The relapse rates will be estimated in patients of the CP analysis groups with EoT response and sufficient HCV RNA measurements post-

treatment. Viral breakthrough rates will be estimated in all patients of the CP analysis groups, who have at least one undetectable HCV RNA measurement on-treatment and at least one on-treatment or EoT measurement thereafter.

Univariate and multiple logistic regression (MLR) methods will be used to investigate the impact of the following explanatory covariates on SVR12:

- Key demographic information
- Mode of CHC infection
- HCV RNA level at baseline
- Most recent stage of liver fibrosis
- HCV genotype and subtype (if available)
- Type of treating institute
- Liver and/or CHC related co-morbidities
- Key clinical chemistry and hematology laboratory variables at baseline
- In treatment experienced patients only:
 - Most recent prior treatment for CHC
 - Outcome of most recent prior CHC treatment

Further details and additional covariates will be specified in the SAP.

These analyses will be of exploratory nature, data driven, and will be repeatedly performed for various CP Analysis Groups, since not each covariate might be predictive in each patient group. Furthermore, the fact that treatment regimens will differ in the various patient groups has to be taken into account, when selecting the patient groups for each MLR analysis. Backward selection procedures will be applied to generate the final MLR models which consider only covariates in the selection procedure with a p-value <0.25 in the corresponding univariate logistic regression analysis. A p-value <0.05 will be used for the covariates to stay in the model in a backward elimination step. Logistic regression methods will also be used to investigate the impact of treatment adherence on SVR12.

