## 4.2 Sample size

The sample size is justified in the clinical study Protocol.

The expected SVR12 rate is 90%. This value is based on results of previous sponsor's studies investigating the interferon-free ABBVIE REGIMEN ± RBV.

 This section is based on the section 9.5 "Study Size" of clinical study Protocol.

The sample size calculation was performed in order to obtain assessments of qualitative features with exact two-sided 95% Clopper-Pearson confidence interval, which doesn't exceed  $\pm 5\%$  (i.e. total spread is not more than 10%) from the point estimate.

With 158 evaluable patients 95% CI will be 84.2%-94.2%, i.e. not more than 10%. Therefore, 158 patients should be enrolled during the inclusion period of 8 months.

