- key demographic information:
  - age;
  - gender;
  - race;
- mode of CHC infection:
  - Most likely mode of HCV infection;
  - HCV Genotype and Subtype;
- HCV RNA level at baseline;
- most recent stage of liver fibrosis:
  - Severity of cirrhosis by Child-Pugh classification;
  - Result of FibroTest;
  - ISHAK Fibrosis Score;
  - METAVIR Fibrosis Score;

- BATTIS/LUDWIG Fibrosis Score;
- KNOPELL Fibrosis Score;
- SCHEUER Fibrosis Score;
- liver and/or CHC related co-morbidities;
- treatment experience (Interferon, Ribavirin, DAA);
- outcome of most recent prior CHC treatment
- laboratory hematology:
  - hemoglobin;
  - platelets;
  - prothrombin time, international normalized ratio (INR);
- laboratory clinical chemistry:
  - ALT;
  - AST;
  - gamma-GT;
  - total bilirubin;
  - albumin;
  - creatinine clearance;
  - alpha-1-fetoprotein.

After univariate model analyses all covariates with a p-value <0.25 in the corresponding univariate logistic regression analysis will be included to multiple logistic regression (MLR) model. MLR will be performing only if more than one explanatory variables will have a p-value <0.25 in the univariate model analyses.

Statistical significant correlated variables with correlation coefficient  $\geq 40$  should be considered and managed. All solutions about choosing explanatory variables will be of exploratory nature, data driven, and will be described with presenting of results of the “*PROC CORR*” SAS procedure.

Backward selection procedures will be applied to generate the final MLR models. A p-value <0.05 will be used for the covariates to stay in the model in a backward elimination step.

The SAS procedure LOGISTIC will be used for the analysis with following statements:

- SELECTION= BACKWARD;
- SLENTRY=0.05.

To avoid the multicollinearity problem all possible explanatory variables will be examined using following SAS script:

```
ods graphics on;  
PROC CORR data=<dataset> plots=all;  
  VAR <variables>;  
RUN;  
ods graphics off;
```

All data for Effectiveness Analyses will be listed in separate listings (for each effectiveness analyses endpoint). Additional listings for NCP population will be created.

---

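### SAP section 9 splits the protocol's one liver-fibrosis covariate into seven method-specific scores, omits FibroScan, and screens 26 candidates against about 8–16 expected SVR12 failures

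*SAP*

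**What the plan says.** Protocol section 9.7.3.3 lists a single fibrosis covariate for the SVR12 regressions, "Most recent stage of liver fibrosis". SAP section 9 places seven items under that heading: "Severity of cirrhosis by Child-Pugh classification", FibroTest, and the Ishak, Metavir, Batts/Ludwig, Knodell and Scheuer histology scores. FibroScan is summarised at baseline (SAP section 8.4 and Table 1.6.1) but is not in the covariate list.

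Each candidate is first tested alone. Then "all covariates with a p-value <0.25 in the corresponding univariate logistic regression analysis will be included" in one multiple model, and "A p-value <0.05 will be used for the covariates to stay in the model in a backward elimination step". On estimation, "The SAS procedure LOGISTIC will be used for the analysis with following statements"; only a backward-selection option and an entry level follow, with no penalised or exact method. The shells for the univariate models (Table 2.2.1.1.1) and the multiple model (Table 2.2.1.2) report Wald intervals. SAP section 7.3 rules out imputation and section 7.5 rules out multiplicity adjustment.

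The regressions are repeated for breakthrough, relapse, failure to suppress and end-of-treatment response, under two response definitions, in subgroups, and in the target population and the core population with sufficient follow-up.

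**The concern.** Two features combine badly. First, PROC LOGISTIC drops any patient with a missing value in any model covariate. The histology scores need a biopsy, which Table 1.6.1 shows as one of three diagnostic routes, and protocol Table 2 collects only what routine care provides. A biopsy score in the model therefore confines it to biopsied patients scored on that system. A patient staged only by FibroScan contributes none of these six stage scores.

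Second, the candidate list is long for the number of failures, so selection by p-value will often keep noise.

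The model serves the secondary objective on predictive factors, and protocol section 7.2 hopes such factors could help optimise treatment. At stake are predictors that do not replicate, or predictors estimated in an unplanned, selected subset.

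**Working it through.** **1. The plan's own figure.** SAP section 4.2 says "The expected SVR12 rate is 90" per cent and "With 158 evaluable patients 95% CI will be 84.2%-94.2%, i.e. not more than 10" per cent. Clopper-Pearson with x = 158 × 0.90 = 142.2 gives 84.23–94.20, width 9.97 points, so it reproduces. Protocol section 9.5 adds: "If the SVR12 rate is at least 95%, then 94 patients are sufficient for a width of 10" per cent. With x = 94 × 0.95 = 89.3 this gives 88.45–98.43, width 9.98.

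**2. Expected failures** = 158 × (1 − SVR12).
- At 90%: 15.8 (95% binomial range 9–24).
- At 95%: 7.9 (range 3–14).

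Protocol section 9.7.1 counts missing HCV RNA as failure. With an assumed missing share m and true failure rate f, the count is 158 × (m + (1 − m)f). For m of 5–10% that is about 23–30 at f = 10% and 15–23 at f = 5%, some of them not virological.

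**3. Candidates in SAP section 9.** Demographics 3, infection mode and genotype 2, baseline HCV RNA 1, fibrosis 7, co-morbidities 1, treatment experience 1, prior outcome 1, haematology 3 (prothrombin time and INR as one), chemistry 7: total 26. Failures per candidate: 15.8/26 = 0.61 and 7.9/26 = 0.30.

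**4. False selection when nothing is predictive.** Expected to pass the screen: 26 × 0.25 = 6.5. Expected below 0.05: 26 × 0.05 = 1.3. Chance of at least one below 0.05 if independent: 1 − 0.95^26 = 0.74.

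Simulating the actual procedure (n = 158, univariate Wald p<0.25, backward at p<0.05, independent noise unless stated), the share of runs with at least one noise predictor in the final model is:

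| Candidates and method | SVR12 90% | SVR12 95% |
|---|---|---|
| 26, ordinary likelihood (1,500 runs) | 69% | 63% |
| 20, ordinary likelihood (1,500 runs) | 58% | 52% |
| 24, ordinary likelihood (500 runs) | 73% | 55% |
| 24, Firth (500 runs) | 66% | 57% |
| 18, Firth (500 runs) | 52% | 43% |
| Two thirds of candidates sharing correlation 0.5 | 61% | 46% |

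Monte Carlo error is about √(0.69 × 0.31/1500) = 1.2 points for the 1,500-run rows and √(0.5 × 0.5/500) = 2.2 points for the 500-run rows. The rest of the spread between rows reflects the number and type of covariates.

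**5. Separation or non-convergence of the first multiple model.** With 26 candidates in 158 patients: 0.1% at SVR12 90% and 3.3% at 95%. In a subgroup of 80 at 95% with 20 candidates: 12%. Rare categorical levels were not modelled.

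**6. Complete-case loss (availability assumed throughout).** If 10–50% of patients had a biopsy, split equally over five scoring systems, each score would cover 158 × 0.10/5 = 3.2 to 158 × 0.50/5 = 15.8 patients, with 0.3–1.6 failures at SVR12 90%. Two such scores together would leave no complete case. Without biopsy scores, seven covariates each 80–95% complete, missing independently, leave 158 × 0.80^7 = 33 to 158 × 0.95^7 = 110 patients.

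**The case against.** Both documents call the analysis exploratory and data driven, and it does not touch the primary SVR12 estimate or its interval. The protocol itself prescribes the 0.25 and 0.05 thresholds and lets the SAP add covariates. SAP section 9 says the listed items can be included, so the list is permissive, and it requires a correlation check. The shells already print the number of patients for both model types, and convergence status for the univariate ones, so a shrunken sample would be visible. All of this stands and limits the stakes. The correlation check is weak, however: its threshold is printed as 40, no action is specified, and scores never taken in the same patient have no computable correlation. The shells show no failure counts.

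A reader might infer that separation will spoil the main model. Step 5 does not support that for the overall SVR12 analysis.

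A reader might also infer that the multiple model will collapse to a handful of patients. The documents give no availability shares, and the screen works against it. A null five-level score available in 5, 10 or 16 patients passed p<0.25 in about 0%, 4% and 9% of simulated runs at 10% failure, and in 0–3% at 5%. At 47 patients (30%) it passed in 14–21%. Very sparse scores mostly remove themselves; moderately available ones are the risk. If fibrosis status in SAP section 6 means the Child-Pugh class, as sections 8 and 9 define it, Child-Pugh would be complete in the core population, but the other six scores would not.

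**Conclusion.** The point holds in a limited form. Splitting one protocol covariate into seven method-specific scores, without FibroScan and without imputation, exposes the multiple model to complete-case loss of unknown size. The comparison is with the protocol supplied; the SAP cites a later version.

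With 26 candidates and about 8–16 expected failures, roughly half to two thirds of null runs would retain a noise predictor. That rests on 158 patients with complete outcomes, SVR12 of 90–95% and independent covariates; correlation lowers it somewhat. Separation is a concern mainly in small subgroups and for the rarer endpoints.

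It would be wrong to read the remedy as a cure for spurious predictors. One fibrosis variable leaves 26 − 7 + 1 = 20 candidates, and null false selection stays at about 50%, because it comes mainly from the selection rule.

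**What to change.** 1. Derive one harmonised fibrosis variable, for example cirrhosis yes/no or an F-stage from whichever method was used, including FibroScan, and enter it in place of the seven scores. SAP section 6 already has to identify cirrhotic patients and excludes those with unknown fibrosis status from the core population, so it should be close to complete there.
2. Fit the sparse models with the FIRTH option and profile-likelihood intervals. This addresses sparse-data bias, not false selection.
3. Add the number of failures beside the patient count in Tables 2.2.1.1.1 and 2.2.1.2.
4. State a minimum number of failures below which no multiple model is fitted. The documents give no figure; a floor of 10 would also bar the overall model at SVR12 95% (7.9 expected).
5. Report retained covariates as hypothesis-generating, and say that about half of null runs would still keep one.

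The cost is one derived variable, one procedure option and one table row. The downside is slightly shrunken odds ratios, fewer subgroup models and some detail lost by pooling fibrosis methods.

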### **7.2 Statistical tests and common calculations**

Unless otherwise specified in the description of the analyses, the following arrangements will be applied:

- all tests will be two-sided with the default significant level 5%;
- confidence intervals will be 95% and will be determined using the Clopper-Pearson method.

Type I error values (p-values) will be rounded to four decimal symbols.

For quantitative measurements of clinical laboratory data, changes from baseline will be calculated as (measurement at visit X – measurement at baseline).

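### The SAP's collinearity trigger is a correlation coefficient of at least 40, which cannot occur; read as 0.40, it still lacks an absolute value and a measure suited to multi-category nominal covariates

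*SAP*

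**What the plan says.** SAP section 9 screens covariates one at a time, carries those with p < 0.25 into a multiple logistic model, and then applies backward elimination at p < 0.05. Between these steps are two provisions on collinearity.

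- **A trigger.** "Statistical significant correlated variables with correlation coefficient" of at least 40 are to be considered and managed. No decimal point, percent sign or absolute value appears. The only significance level given is the default in section 7.2: "all tests will be two-sided with the default significant level 5" percent.
- **An examination.** "To avoid the multicollinearity problem all possible explanatory variables will be examined using following SAS script". The script calls PROC CORR with a data set name, plots=all and a placeholder list of variables. No type of coefficient is requested.

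The section does not say which member of a flagged pair is kept. It says: "All solutions about choosing explanatory variables will be of exploratory nature, data driven, and will be described with presenting of results of the" PROC CORR procedure.

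The candidate list mixes continuous laboratory values, ordinal fibrosis scores and nominal items such as race and "Most likely mode of HCV infection". Protocol section 9.7.3.3 has the same selection steps but no collinearity rule, and no other part of the SAP restates the limit.

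**The concern.** A stated decision limit that no data can reach leaves the programmer to guess what was meant. The obvious guess, 0.40, leaves two gaps. A signed limit treats r = +0.8 as a problem and r = -0.8 as none, although both inflate variance equally. And a Pearson coefficient computed on integer codes for unordered categories changes when the categories are renumbered.

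At stake is which of two related markers survives backward elimination and how wide its interval is. Predictors of virological response are the first secondary objective, and protocol section 7.2 hopes that they could help optimise treatment. The rule that keeps near-duplicate markers out of one model should therefore work as written.

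**Working it through.** There is no derived figure to reproduce here, because the limit is a stated rule. The one planning number used below is N = 158 (SAP section 4.2). Its exact interval at 90% (158 x 0.90 = 142.2 responders) reproduces as 84.2% to 94.2%.

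**1. Can the limit be met?** For any two variables, -1 <= r <= 1. Hence r >= 40 is impossible and the literal rule flags nothing.

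**2. Does the significance condition matter if 0.40 was meant?** The smallest significant |r| at two-sided 5% is t / sqrt(n - 2 + t²), with t on n - 2 degrees of freedom.

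| n | critical abs(r) |
|---|---|
| 158 | 0.156 |
| 30 | 0.361 |
| 20 | 0.444 |

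At full size the condition adds nothing to a 0.40 limit. Of the sizes shown, it exceeds 0.40 only at n = 20, that is, in a small subgroup model.

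**3. What does the missing absolute value do?** Bivariate normal pairs were simulated at N = 158 with 4,000 replicates. The table shows the share flagged.

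| true correlation | r >= 40 | r >= 0.40 | abs(r) >= 0.40 |
|---|---|---|---|
| -0.9 | 0% | 0% | 100% |
| -0.7 | 0% | 0% | 100% |
| -0.5 | 0% | 0% | 94% |
| +0.5 | 0% | 95% | 95% |
| +0.7 | 0% | 100% | 100% |
| +0.9 | 0% | 100% | 100% |

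**4. Are negative pairs to be expected?** The protocol's own definitions imply some among the listed candidates.

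- The Child-Pugh annex gives more points as albumin falls. Child-Pugh and albumin are both candidates.
- Protocol section 9.4.1.1 derives creatinine clearance by the Cockcroft-Gault formula from creatinine, gender, age and weight. That formula falls with age. Age and creatinine clearance are both candidates.

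The definitions give the direction only. The documents do not say how strong these correlations are in this cohort.

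**5. How much would an unhandled pair matter?** For two predictors in a linear model, VIF = 1 / (1 - r²), and the standard error grows by its square root. This is approximate for logistic regression, and the r values are assumptions.

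| abs(r) | VIF | standard error multiplied by |
|---|---|---|
| 0.4 | 1 / 0.84 = 1.19 | 1.09 |
| 0.6 | 1 / 0.64 = 1.56 | 1.25 |
| 0.8 | 1 / 0.36 = 2.78 | 1.67 |
| 0.9 | 1 / 0.19 = 5.26 | 2.29 |

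**6. What does Pearson do with nominal codes?** PROC CORR returns Pearson when no option is given, and its variable list accepts only numeric variables. In a made-up example (four unordered categories, a continuous partner, N = 158), Pearson r over all orderings of the codes ran from -0.61 to +0.61. The coding-free measure, eta, was 0.63. Against a limit of r >= 0.40, the same variable is flagged or missed according to how its categories were numbered.

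**The case against.** The strongest reply is that no analyst would apply a limit of 40 to a coefficient bounded by 1. The meaning is evidently 0.40 or 40%, and the SAP has all candidates examined in a full matrix whatever the limit. Much of this stands. A decimal point lost when the PDF was read cannot be excluded from the text alone, although 0.25 and 0.05 in the same part of section 9 came through intact. The examination prints signed coefficients, so negative pairs would be seen. A reader might infer that the plan has no working check on collinearity, or that negative correlations are ignored altogether. The documents do not support either: the defect is in the trigger, not in what is printed.

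The Pearson point also has limits. The variable list in the script is a placeholder and indicator coding is not ruled out, so the objection applies only if raw integer codes are entered. It does not apply to a two-level split such as genotype 1a or 1b, where Pearson is the phi coefficient and is valid. The table-shell footnotes put patients with combined genotypes in separate subgroups, so a third level could arise.

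Finally, unstable predictors should not be blamed on this rule alone. At 90% SVR12, 158 patients yield about 16 non-responders (158 x 0.10 = 15.8) against 26 listed candidates, counting each entry once. Selection would be fragile even with a perfect collinearity rule.

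What remains is that the written limit is wrong, nothing elsewhere corrects it, and reading it as 0.40 does not supply the absolute value.

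**Conclusion.** The point holds as a correctable fault in a stated decision rule. As written the trigger can never act. Read as 0.40, it still passes over strong negative pairs and has no suitable measure for nominal covariates with more than two categories entered as codes.

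The effect is confined to the exploratory logistic models. A reader might infer that the main result is at risk. It is not, because the SVR12 percentage and its Clopper-Pearson interval use no covariates.

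The size depends on correlations that the documents do not give. Under the assumed values, the standard error grows by 9% at |r| = 0.4, which is minor, and by a factor of 2.29 at |r| = 0.9, which is not. The conclusion assumes that the printed 40 is what the signed SAP contains, and that the script runs with the default coefficient.

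**What to change.** Replace the trigger sentence in SAP section 9, and amend the script to match, along these lines:

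> Association between candidate covariates will be assessed by Spearman correlation for continuous or ordinal pairs, Cramer's V for pairs of nominal covariates, and eta for a nominal covariate paired with a continuous or ordinal one. Pairs with an absolute correlation, Cramer's V or eta of at least 0.40 will be listed and reviewed. The choice of which covariate to retain, or to retain both, will be made and documented without regard to their relation with SVR12. Variance inflation factors will be reported for the starting multiple model.

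If another limit was intended, state it in place of 0.40. Review is preferable to an automatic bar, because at 0.40 the variance inflation factor is only 1.19 and useful candidates could be discarded for little gain. The significance condition may stay; at 158 patients it changes nothing.

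The cost is one SAP paragraph and a little extra output. No new data are needed. SAP section 2 allows revision before database soft lock; after that, the change would be explained in the study report.
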